6.3 Withdrawal criteria

Subjects are free to withdraw from the study at any time, without prejudice to their continued care.

Subjects **must** be withdrawn from this study if any of the following events occur:

1. Subject experiences intolerable AEs, including clinically relevant abnormal laboratory findings that, in the opinion of the investigator, preclude further participation in the study.
2. The sponsor or a regulatory agency requests withdrawal of the subject.
3. Subject has QTc interval ≥ 500 ms that is confirmed by a cardiologist overread on any ECG.
4. Subject develops a second degree atrioventricular (AV) block while awake or develops a third degree AV block.
5. For subjects ≥ 6 years of age, subject has actual suicidal ideation since last visit as indicated by a positive response ("Yes") to either Question 4 or Question 5 of the C-SSRS. The subject should be referred immediately to a Mental Healthcare Professional and must be withdrawn from the study.

6. Subject is unwilling or unable to continue, or the parent/legal representative is unwilling or unable to allow the subject to continue in the study.
7. Investigator decides that withdrawal from further participation would be in the subject's best interest.
8. Subject experiences convulsive status epilepticus.
9. Subject uses rescue medication in excess of that permitted by the protocol.
10. In the case of liver function test (LFT) results of transaminases (AST, ALT, or both) $\geq 3x$ ULN to $< 5x$ ULN and total bilirubin $\geq 2x$ ULN or transaminases (AST, ALT, or both) $\geq 5x$ ULN, the study medication must be immediately discontinued and the subject withdrawn from the study. The LFTs will be repeated as soon as possible, and in no case > 1 week later.
11. Female subject who achieves menarche and does not practice contraception as provided in Exclusion Criteria 6 unless sexually abstinent. Subject becomes pregnant, as evidenced by a positive pregnancy test.
12. Subject needs any alteration in AED daily dose or VNS settings.

Participation in this study may be discontinued for any of the following reasons:

1. Subject has any clinically relevant change in medical or psychiatric condition (if in the opinion of the investigator, the change in condition warrants discontinuation from the study).
2. Subject requires a medication that is not permitted by the protocol.
3. Subject and/or delegated caregiver is noncompliant with study procedures or medication, in the opinion of the investigator.

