7.2.4 Taper Period (for subjects not entering EP0034)

A blinded Taper Period (2 to 4 weeks, depending on dose achieved) will be required for subjects who discontinue study medication prematurely and for subjects who complete the Maintenance Period but choose not to enter the open-label extension study (EP0034).

Table 7-5 provides the taper steps based on the dose of LCM (or matching placebo) achieved. A slow taper is permitted if medically necessary. Whenever possible, these cases should be discussed with the medical monitor prior to withdrawing the subject from the study, especially in cases in which withdrawal criteria have been met. In case of an emergency, a faster taper is permitted after discussion with the medical monitor, whenever possible. Taper of LCM may not be required for some subjects who discontinue study medication prematurely, depending on the treatment option selected by the investigator in consultation with the subject and/or parent/legal representative.

Table 7–5: Taper Period dosing of LCM (or matching placebo)

LCM (or matching placebo) dose achieved	LCM (or matching placebo) doses for the Taper Period			
	Week 17	Week 18	Week 19	Week 20
11 or 12mg/kg/day	9mg/kg/day	6mg/kg/day	4mg/kg/day	2mg/kg/day
9 or 10mg/kg/day	8mg/kg/day	6mg/kg/day	4mg/kg/day	2mg/kg/day
7 or 8mg/kg/day	6mg/kg/day	4mg/kg/day	2mg/kg/day	2mg/kg/day
5 or 6mg/kg/day	4mg/kg/day	2mg/kg/day	2mg/kg/day	NA
3 or 4mg/kg/day	2mg/kg/day	2mg/kg/day	NA	NA
2mg/kg/day	NA	NA	NA	NA
350 or 400mg/day	300mg/day	200mg/day	100mg/day	100mg/day
250 or 300 mg/day	200mg/day	100mg/day	100mg/day	NA
150 or 200mg/day	100mg/day	100mg/day	NA	NA
100mg/day	NA	NA	NA	NA

LCM=lacosamide; NA=not applicable (taper not required)

Note: The oral solution is dosed as mg/kg/day and tablets are dosed as mg/day.

Note: Subjects not requiring taper will enter directly into the Safety Follow-Up Period and not attend any Taper Period visits.

Note: The subject's body weight at Baseline (Visit 2) will be used to determine dose throughout the study.

Note: The study week numbers provided are for subjects who complete the Maintenance Period and enter the Taper Period. The study week numbers provided do not apply to subjects who enter the Taper Period at other times.

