8.5 Taper Period

A blinded Taper Period (2 to 4 weeks, depending on dose achieved) will be required for subjects who discontinue study medication prematurely and for subjects who complete the

Maintenance Period but choose not to enter the open-label extension study (EP0034). Taper of LCM may not be required for some subjects who discontinue study medication prematurely depending on the treatment option selected by the investigator in consultation with the subject and/or parent/legal representative. The Taper Period is not required for subjects who complete the Maintenance Period and who do not undergo taper of LCM.

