8.8 Early Termination Visit

Subjects who withdraw from the study prematurely for any reason, including AEs, must complete an Early Termination Visit. At the time of withdrawal from the study, investigators should discuss treatment options with the subject and/or their parent/legal guardian to best manage the subject's epilepsy. Taper of LCM may not be required for some subjects who discontinue study medication prematurely, depending on the treatment option selected by the investigator in consultation with the subject and/or parent/legal guardian. These subjects should complete the Early Termination Visit and then complete the 30-day Safety Follow-Up Period.

The following assessments should be completed at the Early Termination Visit and prior to subjects entering the blinded Taper Period (2 to 4 weeks).

- Concomitant medications
- Concomitant AEDs
- Changes in VNS settings
- Physical examination (complete)
- Tanner Stage assessment
- Vital signs (BP and pulse rate, including orthostatic assessments)
- Body weight assessment
- Height assessment
- Head circumference
- Neurological examination (complete)
- 12-lead ECG (2 interpretable recordings to be performed prior to any blood draws and vital signs assessment and, if possible, with the subject in the supine position for approximately 5 minutes preceding the recordings and during the recordings)
- Blood sample for clinical chemistry and hematology
- Blood sample for endocrinology
- Urine sample for urinalysis (for subjects ≥ 5 years of age)
- Serum pregnancy test (for females of childbearing potential)
- Blood sample for measurement of concomitant AED plasma concentrations
- Blood sample for measurement of LCM plasma concentration
- C-SSRS (for subjects ≥ 6 years of age)
- Clinical Global Impression of Change
- Caregiver's Global Impression of Change
- Achenbach CBCL (same version used at Visit 2)
- BRIEF-P/BRIEF score (version consistent with that used at Visit 2)
- PedsQL score (version consistent with that used at Visit 2)
- Contact IXRS
- Dispense study medication for the Taper Period (2 to 4 weeks)
- Study medication return
- Reminder to complete subject diary on a daily basis
- AE reporting
- Health care resource use

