11.7 Liver function tests

Refer to Section 6.3 for LFT withdrawal criteria.

Transaminases (AST, ALT, or both) $\geq 3 \times \text{ULN}$ but $< 5 \times \text{ULN}$, in the presence of total bilirubin $\geq 2 \times \text{ULN}$, or transaminases (AST, ALT, or both) $\geq 5 \times \text{ULN}$ will result in immediate discontinuation of study medication and withdrawal of the subject from the study. The LFTs will be repeated as soon as possible, and in no case more than 1 week later.

Transaminases (AST, ALT, or both) $\geq 3 \times \text{ULN}$ to $< 5 \times \text{ULN}$, in the presence of normal total bilirubin, will be repeated within a few days. If the repeat testing confirms the abnormality (ie, transaminases are $\geq 3 \times \text{ULN}$ to $< 5 \times \text{ULN}$ with normal bilirubin), then weekly monitoring of LFTs should continue until resolved (ie, $< 3 \times \text{ULN}$ or stable condition). The investigator is to decide whether or not to stop the study medication.

In all cases of transaminases (AST, ALT, or both) $\geq 3 \times \text{ULN}$, testing for hepatitis A, B, and C will be done.

Referral to a specialist (ie, hepatologist or gastroenterologist) is at the discretion of the investigator. This is recommended especially if the transaminase abnormalities $>3xULN$ persist after discontinuation of the study medication.

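### The liver-test criterion requires an immediate stop of study medication, but taper is the default after premature discontinuation, and the discretionary exemption from taper is never tied to that criterion

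*Protocol*

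**What the plan says.** **Stop rule.** Protocol 6.3, criterion 10, covers transaminases from 3 to below 5 times ULN with total bilirubin at least 2 times ULN, or transaminases at least 5 times ULN. In that case "the study medication must be immediately discontinued and the subject withdrawn from the study". Section 11.7 says the same results "will result in immediate discontinuation of study medication and withdrawal of the subject from the study". Both ask for repeat liver tests as soon as possible and within 1 week. Neither mentions taper.

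**Taper default.** Section 7.2.4 states: "A blinded Taper Period (2 to 4 weeks, depending on dose achieved) will be required for subjects who discontinue study medication prematurely". Section 8.5 and note a of Table 5-3 say the same. Section 8.2 sends a subject whose study medication has to be withdrawn during titration into the Taper Period. Section 8.8 applies to withdrawal for any reason, including adverse events, and its list for the Early Termination Visit includes "Dispense study medication for the Taper Period (2 to 4 weeks".

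**Exemption.** Section 7.2.4 adds: "Taper of LCM may not be required for some subjects who discontinue study medication prematurely, depending on the treatment option selected by the investigator". Equivalent sentences stand in 5.1, 7.2.2, 8.5 and 8.8 and in the notes to Tables 5-1 and 5-3. For subjects who do not taper, 8.8 gives the route: "These subjects should complete the Early Termination Visit and then complete the 30-day Safety Follow-Up Period".

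**Other provisions.** For emergencies, 7.2.4 permits a faster taper and does not mention stopping outright. For pregnancy, 11.1.6 names both routes: an immediate stop or a down-titration as instructed at the Early Termination Visit.

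**The concern.** A mandatory safety stop in a paediatric trial should lead to one action at every site. Here the stop rule is silent on taper, and the taper rules are silent on the stop rule. Two investigators with the same liver result could each cite the protocol, one for stopping that day and the other for dispensing up to 4 weeks of blinded medication.

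Three things depend on the reading:

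- whether a child with a stopping-level result takes further lacosamide;
- whether the mandated repeat test measures recovery off drug or liver values under continued, reduced exposure;
- where the safety windows fall. SAP 3.2.1.1 counts taper doses when it defines the last dose, and the treatment-emergent window in SAP 10.2 runs 30 days from that date.

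**Working it through.** The documents give no figure to reproduce, so the check sets the passages side by side and then bounds the exposure from Table 7-5.

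**1. Can both sets of passages be followed?** Yes. A site can stop the drug under criterion 10, use the exemption in 7.2.4, 8.5 and 8.8, and move the subject from the Early Termination Visit to Safety Follow-Up.

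**2. Does any passage direct the site to that route after a liver-test stop?** No.

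- The exemption covers some subjects and depends on the treatment option the investigator selects with the family. The scheduling text at the end of 8.8 likewise attributes non-taper to other treatment options, not to a safety stop.
- Section 7.2.4 discusses taper in cases where withdrawal criteria have been met and does not carve out criterion 10.
- The 8.2 sentence has no exemption beside it. Clinical chemistry is drawn at Visits 4 and 5, both in titration, so a criterion 10 result can arise where 8.2 applies.
- The dispensing item in 8.8 lacks the qualifier (as applicable) that the matching item at Visit 8 carries in 8.3.3.
- The pregnancy section shows that the protocol can state both routes when it means to.

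**3. Exposure if the default is followed.** Assumptions: the subject is on lacosamide, each Table 7-5 step lasts 7 days, and the taper is completed.

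Lacosamide taken in taper = 7 × (sum of the weekly daily doses).

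| Dose achieved | Weekly taper doses | Total | Days |
|---|---|---|---|
| 11 or 12mg/kg/day | 9, 6, 4, 2 | 7 × 21 = 147mg/kg | 28 |
| 9 or 10mg/kg/day | 8, 6, 4, 2 | 7 × 20 = 140mg/kg | 28 |
| 7 or 8mg/kg/day | 6, 4, 2, 2 | 7 × 14 = 98mg/kg | 28 |
| 5 or 6mg/kg/day | 4, 2, 2 | 7 × 8 = 56mg/kg | 21 |
| 3 or 4mg/kg/day | 2, 2 | 7 × 4 = 28mg/kg | 14 |
| 2mg/kg/day | none | 0 | 0 |
| 350 or 400mg/day | 300, 200, 100, 100 | 7 × 700 = 4900mg | 28 |
| 250 or 300mg/day | 200, 100, 100 | 7 × 400 = 2800mg | 21 |
| 150 or 200mg/day | 100, 100 | 7 × 200 = 1400mg | 14 |
| 100mg/day | none | 0 | 0 |

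The maxima equal 147/12 = 4900/400 = 12.25 days at the full dose. The 147mg/kg figure can arise only below 30kg, because Table 7-1 caps the 30 to below 50kg group at 8mg/kg/day (98mg/kg in taper).

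**4. Dose at the repeat test.** If taper starts at once, a test within 7 days falls in the first taper step. From 12mg/kg/day or 400mg/day that step is 9/12 = 300/400 = 75% of the dose achieved. Across Table 7-5 it ranges from 50% (4 to 2mg/kg/day, or 200 to 100mg/day) to 89% (9 to 8mg/kg/day). A 28-day taper would run about 3 weeks beyond the test.

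**5. Follow-up windows.** With an immediate stop, the 30-day treatment-emergent window starts at the stop. After a 28-day taper it ends 28 + 30 = 58 days after the stop decision. The Safety Follow-Up Visit, set at 2 weeks after the final dose, moves by the same 28 days.

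**The case against.** The strongest reply is that the protocol contains a default with an exception, together with a specific mandatory rule, and that such a set can be read coherently. The exemption appears in many places, and 8.8 states it before its checklist. Criterion 10 is the only one of the 12 mandatory withdrawal criteria that orders immediate discontinuation of medication, which supports reading it as the more specific instruction. There are also safeguards: 6.3 and 7.2.4 ask for contact with the medical monitor whenever possible, and 12.1 lets the investigator act against an immediate hazard.

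Much of this stands, and it rules out several stronger readings:

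- A reader might infer that taper is required with no exemption. The exemption and the no-taper route show otherwise.
- A reader might infer that a site stopping immediately breaches the taper rules. It does not, if it uses the exemption.
- A reader might take 147mg/kg or 4900mg as the expected consequence. They are top-row maxima, and the documents give no expected frequency of criterion 10 events.
- A reader might infer that persistence after discontinuation, which 11.7 mentions when recommending referral, cannot be judged under taper. That sentence has no deadline, so the assessment is at most delayed.

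The gap itself is not answered. The specific-over-general reading is reasonable, but no passage states it. Contact with the medical monitor is asked for only when possible, and a mandatory stop still depends on an option that is worded for a different purpose.

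**Conclusion.** The point holds as an unreconciled safety instruction. It is not a case of two mandates that cannot both be met. Sections 6.3 and 11.7 require an immediate stop; the taper and Early Termination passages make taper the default; and the only way out is discretionary and not tied to criterion 10. A site that follows the default would continue dosing after the mandated stop and draw the repeat liver test during taper.

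The size is bounded: up to 147mg/kg or 4900mg over 28 days for lacosamide subjects on the top rows, less on lower rows. It is zero for subjects at 2mg/kg/day or 100mg/day, who have no taper, and placebo subjects would take only matching placebo. These figures assume a full taper in 7-day steps. How often the situation would arise cannot be derived from the documents.

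The point bears on patient safety and on the timing of safety follow-up. The check identified no effect on the primary efficacy analysis. It should be corrected.

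**What to change.** Reconcile 6.3 criterion 10, 11.7, 7.2.4, 8.2, 8.5 (with note a of Table 5-3) and 8.8 so that one passage states whether the Taper Period applies after a liver-test stop. Cross-reference that passage from the taper and Early Termination sections. Align the dispensing item for the Early Termination Visit and the IXRS with it, so that the system and the checklist give the same instruction as the text. The sponsor's clinical team must decide what the rule is; no rule is proposed here.

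The cost is a protocol wording change plus a flag in the IXRS and the Early Termination checklist. Sample size and the planned analyses do not change.

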4. Subject needs any alteration in AED dosing frequency.
5. Transaminases (AST, ALT, or both) $\geq 3x$ ULN to $< 5x$ ULN, in the presence of normal total bilirubin, will be repeated within a few days. If the repeat testing confirms the abnormality (ie, transaminases are $\geq 3x$ ULN to $< 5x$ ULN with normal bilirubin), then weekly monitoring of LFTs should continue until resolved (ie, $< 3x$ ULN or stable condition). The investigator is to decide whether or not to stop the study medication.

Investigators should attempt to obtain information on subjects, in the case of withdrawal or discontinuation. For subjects considered as lost to follow-up, the investigator should make every effort (≥ 1 phone call and 1 written message to the parent[s] or legal representative), and document his/her effort (date and summary of the phone call and copy of the written message in the source documents) to complete the final evaluation. All results of these evaluations and observations, together with a narrative description of the reason(s) for removing the subject, must be recorded in the source documents. The Case Report form (CRF) must document the primary reason for withdrawal or discontinuation.

Investigators should contact the Medical Monitor whenever possible to discuss the withdrawal of a subject in advance.

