8 STUDY PROCEDURES BY VISIT

Detailed tabular schedules of study procedures are provided in Section 5.2. The subject should take concomitant AEDs at the usual time(s) on the morning of each clinic visit.

At all visits and telephone contacts, subjects will be instructed to call the investigator if any intolerable and/or serious AEs occur before the next visit or contact. After subjects begin study medication, if any AEs necessitate a subject's withdrawal from the study, the subject should come in for a clinic visit as soon as possible after the occurrence of the AE.

Planned clinic visits should be scheduled as indicated in Section 5.2 with a window of ± 2 days relative to Visit 2 (Baseline Period), with the exception of the Safety Follow-Up Visit, which should be scheduled 14 days (-1/+3 days) after the final dose of study medication.

The subject's body weight at Baseline (Visit 2) will be used to determine dose throughout the study.

8.1 Baseline Period: Week -8 to Week 0

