At each clinic visit and telephone contact, the investigator, in conjunction with the subject and/or parent(s)/legal representative(s), will decide how to proceed with study medication dosing based on tolerability (including vital signs, body weight, 12-lead ECG, and AE reporting, as applicable to the type of contact). If the withdrawal of study medication is required during the Titration Period, the subject will enter the blinded Taper Period (Section 8.5).

8.2.1 Titration Period: Telephone Contact 2 (Week 1), Telephone Contact 3 (Week 3), and Telephone Contact 4 (Week 5)

During the Titration Period telephone contacts (Telephone Contact 2, Telephone Contact 3, and Telephone Contact 4), the following assessments will be performed:

- Concomitant medications
- Concomitant AEDs
- Reminder to complete subject diary on a daily basis
- Review withdrawal criteria
- AE reporting

8.2.2 Titration Period: Visit 3 (Week 2), Visit 4 (Week 4), and Visit 5 (Week 6)

During the Titration Period clinic visits (Visit 3, Visit 4, and Visit 5), the following assessments will be performed:

- Concomitant medications
- Concomitant AEDs
- VNS assessment (for subjects with an implanted VNS device)
- Physical examination (brief)
- Vital signs (BP and pulse rate, including orthostatic assessments)
- Body weight assessment
- Neurological examination (brief)
- 12-lead ECG (2 interpretable recordings [20 to 30 minutes apart] to be performed prior to any blood draws and vital signs assessment and, if possible, with the subject in the supine position for approximately 5 minutes preceding the recordings and during the recordings)
- Blood sample for clinical chemistry and hematology (Visit 4 and Visit 5 only)
- Urine sample for urinalysis (for subjects ≥ 5 years of age) (Visit 4 and Visit 5 only)
- Serum pregnancy test (for females of childbearing potential) (Visit 4 and Visit 5 only)
- Urine pregnancy test (for females of childbearing potential) (Visit 3 only)
- Blood sample for determination of concomitant AED plasma concentration (Visit 5 only)

- Blood sample for determination of LCM plasma concentration (Visit 5 only)
- C-SSRS (for subjects ≥ 6 years of age)
- Achenbach CBCL (same version used at Visit 2) (Visit 5 only)
- Contact IXRS
- Dispense study medication
- Study medication return
- Reminder to complete subject diary on a daily basis
- Review withdrawal criteria
- AE reporting
- Health care resource use

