8.3.1 Maintenance Period: Visit 6 (Week 8) and Visit 7 (Week 12)

During Visit 6 and Visit 7 (clinic visits) of the Maintenance Period, the following assessments will be performed:

- Concomitant medications
- Concomitant AEDs
- VNS assessments (for subjects with an implanted VNS device)
- Physical examination (brief)
- Vital signs (BP and pulse rate; including orthostatic assessments)
- Body weight assessment
- Neurological examination (brief)

- 12-lead ECG (2 interpretable recordings [20 to 30 minutes apart] to be performed prior to any blood draws and vital signs assessment and, if possible, with the subject in the supine position for approximately 5 minutes preceding the recordings and during the recordings)
- Blood sample for clinical chemistry and hematology (Visit 7 only)
- Urine sample for urinalysis (for subjects ≥ 5 years of age) (Visit 7 only)
- Serum pregnancy test (for females of childbearing potential) (Visit 7 only)
- Urine pregnancy test (for females of childbearing potential) (Visit 6 only)
- C-SSRS (for subjects ≥ 6 years of age)
- Contact IXRS
- Dispense study medication
- Study medication return
- Reminder to complete subject diary on a daily basis
- Review withdrawal criteria
- AE reporting
- Health care resource use

The subject will be scheduled to return to the clinic as specified in [Table 5-1](#). The morning of the next clinic visit, the subject should take concomitant AEDs and study medication at the usual time(s).

8.3.2 Maintenance Period: Telephone Contact 5 (Week 10) and Telephone Contact 6 (Week 14)

During the Maintenance Period telephone contacts (Telephone Contact 5 and Telephone Contact 6); the following assessments will be performed:

- Concomitant medications
- Concomitant AEDs
- Reminder to complete subject diary on a daily basis
- Review withdrawal criteria
- AE reporting

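### At transaminases ≥3x to <5xULN with total bilirubin above normal but <2xULN, Protocol 6.3 and 11.7 set no dated LFT repeat and no weekly monitoring for a child kept on study drug

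*Protocol*

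**What the plan says.** Protocol 6.3 has two rules for transaminases (AST, ALT or both) between 3x and 5xULN, separated by total bilirubin.

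- **Must-withdraw criterion 10** applies when total bilirubin is ≥2xULN. Study drug stops, the subject is withdrawn, and "The LFTs will be repeated as soon as possible, and in no case > 1 week later". The same rule applies at transaminases ≥5xULN whatever the bilirubin.
- **May-discontinue item 5** applies when bilirubin is normal. The transaminases, "in the presence of normal total bilirubin, will be repeated within a few days". If the repeat confirms the range "with normal bilirubin), then weekly monitoring of LFTs should continue until resolved". The investigator decides whether to stop the drug.

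Protocol 11.7 restates both rules with the same limits. It adds that for every case ≥3xULN "testing for hepatitis A, B, and C will be done", and leaves specialist referral to the investigator.

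After the first dose, chemistry is drawn at few of the clinic visits. Protocol 8.2.2 (Titration) lists "Blood sample for clinical chemistry and hematology (Visit 4 and Visit 5 only" and 8.3.1 (Maintenance) lists "Blood sample for clinical chemistry and hematology (Visit 7 only", so Visit 6 has none. Further draws are at Visit 8 (8.3.3), then at Transition Visit 4 (8.4.2) or the Taper Visit (8.5.2).

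**The concern.** The two rules do not meet. One needs normal bilirubin and the other needs at least 2xULN; a value between satisfies neither. The order of protection is therefore inverted. At the same transaminase level, a child with normal bilirubin must be retested within days and a child with bilirubin ≥2xULN within a week, but a child with mildly raised bilirubin has no LFT repeat date.

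The confirmation clause has the same fault. Weekly monitoring depends on the repeat again showing normal bilirubin. Read literally, a child whose bilirubin rises from normal to, say, 1.5xULN between the first test and the repeat loses the trigger for weekly monitoring as the picture worsens.

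What is at stake is early recognition of progressing liver injury in children taking study drug with 1 to 3 other antiepileptic drugs. Efficacy is not involved.

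**Working it through.** **Step 1. Coverage of the rules at transaminases ≥3x to <5xULN** (Protocol 6.3 and 11.7; I take *normal* to mean at or below ULN, which the protocol does not spell out).

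| Total bilirubin | Required LFT repeat | Weekly monitoring | Stopping drug |
|---|---|---|---|
| Normal | within a few days | yes, if confirmed | investigator decides |
| Above normal, <2xULN | none stated | none stated | investigator decides (general criteria) |
| ≥2xULN | at most 7 days | not stated | mandatory |

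In the middle row, the only action that 6.3 and 11.7 require is hepatitis A, B and C testing. That looks for a viral cause; it does not show whether the transaminases or bilirubin are rising. Stopping in that row rests on must-withdraw criteria 1 and 7 and may-discontinue item 1, all matters of investigator judgement.

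**Step 2. Wait for the next fixed LFT if nothing extra is ordered.** The inputs are the chemistry visits in Table 5-1, Table 5-2, Table 5-3 and Section 8, in days from Visit 2 (week × 7): Visit 4 = 28, Visit 5 = 42, Visit 7 = 84, Visit 8 = 112, Transition Visit 4 = 140. For Maintenance completers, Table 7-5 tapers 5 or 6mg/kg/day, or 250 or 300mg/day, over 3 weeks, and higher doses over 4 weeks. The lowest Maintenance doses are 6mg/kg/day and 300mg/day, so the Taper Visit falls at day 133 or 140.

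Gap = later day − earlier day. Each visit has a window of ±2 days relative to Visit 2, so each gap can vary by ±4 days.

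| Result first seen at | Next fixed chemistry | Gap (days) | With windows |
|---|---|---|---|
| Visit 4 | Visit 5 | 42 − 28 = 14 | 10 to 18 |
| Visit 5 | Visit 7 | 84 − 42 = 42 | 38 to 46 |
| Visit 7 | Visit 8 | 112 − 84 = 28 | 24 to 32 |
| Visit 8 | Transition Visit 4 | 140 − 112 = 28 | 24 to 32 |
| Visit 8 | Taper Visit, 3-week taper | 133 − 112 = 21 | 17 to 25 |
| Visit 8 | Taper Visit, 4-week taper | 140 − 112 = 28 | 24 to 32 |

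I leave out Visit 2 to Visit 4. The Visit 2 sample is pre-dose, and transaminases ≥3xULN there would breach exclusion criterion 10, which bars ALT, AST or total bilirubin ≥2xULN.

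**Step 3. Subjects who are withdrawn.** The gap does not arise for them. Protocol 8.8 says "Subjects who withdraw from the study prematurely for any reason, including AEs, must complete an Early Termination Visit", and chemistry is on that visit's list. For a withdrawal due to an AE, Section 8 adds that "the subject should come in for a clinic visit as soon as possible after the occurrence of the AE". Chemistry is drawn again at the Taper Visit if the subject tapers, and at the Safety Follow-Up Visit if the previous value was abnormal (8.6.1).

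**The case against.** The strongest reply is that several safeguards surround this child, and that the worst case needs an uncommon laboratory combination, a decision to continue the drug, and an investigator who orders no repeat despite mandatory hepatitis testing.

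Much of that is fair. A reader might infer from the gap that there is no way to stop the drug in this band. The documents do not support that. With normal bilirubin the decision is also the investigator's, and must-withdraw criteria 1 (intolerable AEs, including laboratory findings) and 7 (best interest) and may-discontinue item 1 give the same discretion here.

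A reader might also infer that the 42 days after Visit 5 pass without clinical review. They do not. Visit 6, nominally 14 days later, includes a brief physical examination that covers the abdominal (hepato-gastrointestinal) and dermatologic systems (8.3.1, 11.9.1.2). Telephone Contact 5 at Week 10 collects AEs and reviews withdrawal criteria (8.3.2). Neither includes an LFT.

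Other protections also remain:

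- AE follow-up to resolution or stability (11.1.4).
- Optional tests at unscheduled visits (8.7).
- Periodic sponsor review (11.1.8).
- Special-interest reporting when ALT or AST ≥2xULN occurs with fever, rash, lymphadenopathy or eosinophilia (11.3).
- Real-time triage by the medical monitor and Drug Safety, with referral to the IDMC as appropriate (SAP 4.3). The events triaged include the hepatotoxicity terms in SAP 12.2, provided an AE is reported under them.

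None of these sets a date for repeating LFTs. Nor does reliance on good clinical judgement settle the matter, because the protocol chose not to leave the milder, normal-bilirubin case to judgement.

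**Conclusion.** The concern stands as a gap in monitoring, not in stopping. For a subject kept on drug with transaminases ≥3x to <5xULN and bilirubin above normal but <2xULN, no LFT repeat and no weekly monitoring are prescribed. The next fixed test is then 14 to 42 days away on nominal timing (10 to 46 with visit windows), against a few days with normal bilirubin and at most 7 days at ≥2xULN. The 42 days applies only to a result first seen at Visit 5.

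These are upper limits. They assume that the subject stays on study drug, that the standard taper applies where relevant, and that the investigator orders nothing extra. The documents give no frequency for the combination. Few subjects are likely to be affected, since entry excludes ALT, AST or bilirubin ≥2xULN. No efficacy conclusion changes. This is a cheap improvement to patient safety.

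**What to change.** In Protocol 6.3 (may-discontinue item 5) and in 11.7, make two replacements:

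- In the repeat clause, change *normal total bilirubin* to *total bilirubin <2xULN*.
- In the confirmation clause, change *normal bilirubin* to *total bilirubin <2xULN*.

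Every result ≥3xULN then falls under one of the two rules, using the protocol's own 2xULN cut, and a rise in bilirubin on repeat no longer removes weekly monitoring. No mandatory stop is added. A stricter rule for this band, such as drug interruption, could also be defended, and the documents do not show which was intended; this is the minimum that closes the gap.

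The cost is two phrases in each of two sections, and a few extra repeat blood draws in children.
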